19.9 SAFETY ANALYSES

19.9.1 Safety Population

The Safety Population will consist of all patients who have received a single dose of study medication, i.e., this same population will be used both for the efficacy and safety evaluations. The Safety Population will be used in all safety analyses.

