The incidence of AEs will be summarized through the presentation of proportions by MedDRA body system classification and preferred term. Vital signs and laboratory data will be summarized using continuous-based descriptive statistics (n, mean, SD, median, minimum, maximum). The extent and duration of use of rescue medications will be similarly summarized using descriptive statistics. Summary statistics for AEs with onset during the Observation Period will be separately summarized. No formal statistical analysis will be performed on safety outcomes; inferences, if any, will be derived through clinical review and interpretation.

TABLE OF CONTENTS

1	STUDY SYNOPSIS	5
	TABLE OF CONTENTS	13
	LIST OF TABLES	16
	LIST OF FIGURES	16
2	LIST OF ABBREVIATIONS	17
3	INTRODUCTION	19
3.1	PRURIGO NODULARIS AND STUDY RATIONALE	19
3.1.1	General Information on Prurigo Nodularis	19
3.1.2	Potential Mechanism of Prurigo Nodularis Pathophysiology	21
3.1.3	Rationale for Investigating Nalbuphine HCl ER in Prurigo Nodularis	24
3.2	NALBUPHINE	27
3.3	NALBUPHINE HCL ER TABLET CLINICAL DEVELOPMENT	28
3.3.1	Overall Summary	28
3.3.2	Clinical Study TR01 in Hemodialysis Patients and Healthy Volunteers	29
3.3.3	Additional Nalbuphine HCl ER Tablet Clinical Data	31
4	STUDY OBJECTIVES	32
4.1	PRIMARY OBJECTIVE	32
4.2	SECONDARY OBJECTIVES	32
4.3	EXPLORATORY OBJECTIVES	32
5	STUDY ENDPOINTS	33
5.1	PRIMARY ENDPOINT	33
5.2	SECONDARY ENDPOINTS	33
5.3	EXPLORATORY ENDPOINTS	33
6	NUMBER OF SITES AND PATIENTS	34
7	ESTIMATED STUDY DURATION	34
8	SELECTION CRITERIA	34
8.1	STUDY POPULATION	34
8.2	INCLUSION CRITERIA	34
8.3	EXCLUSION CRITERIA	35
9	STUDY PLAN	35
9.1	GENERAL STUDY DESIGN	35
9.2	RATIONALE FOR STUDY DESIGN	35
9.3	SAFETY MONITORING PLAN	37
9.4	RISK-BENEFITS	39
9.5	STUDY OVERVIEW	40
9.6	STUDY PROCEDURES	42
9.6.1	Visit 1a (Day 1 of Study Week 1)	43
9.6.2	Treatment Period (Treatment Weeks 1-50)	45
9.6.3	Observation Period (Extended Screening Weeks 1-12)	58
9.6.4	Transition to Treatment Period (Visit 1b)	59
9.6.5	Washout and Safety Follow-Up Period	61

9.6.6	Premature Discontinuation of Study Drug Follow-up Telephone Contact Visit	62
9.6.7	Early Termination Visit for Patients who Withdraw Consent.....	62
9.6.8	Unscheduled Visits	63
9.6.9	Schedule of Events.....	63
9.7	STUDY DRUG TREATMENT AND DRUG ACCOUNTABILITY.....	63
9.7.1	Study Drug Dosing	63
9.7.2	Down-Titration	66
9.7.3	Multiple Missed Doses	66
9.7.4	Overdose	66
9.7.5	Treatment Compliance.....	66

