Patients can enroll into TR03ext and receive drug as early as approximately 2 weeks following their last dose of study drug in the parent study TR03. Approximately one-third of patients are expected to enter the study after having received placebo in TR03. These patients are expected to have a high level of pruritus intensity. On the other hand, some patients who have received active treatment in TR03 may still have either reverted to their original pruritic conditions or may have a residual anti-pruritic effects from the drug treatment even following the 2-week wash out period. To allow for various starting levels of pruritus intensity, patients who have Worst Itch NRS that is ≥ 5 will enter the Treatment Period upon completion of Visit 1a. Patients whose Worst Itch NRS score is < 5 will be entered into an extended screening period, no-treatment criteria Observation Period for up to 12 weeks or until they develop a higher level of pruritus (i.e., Worst Itch NRS ≥ 5), at which point they will transition to the Treatment Period upon completion of Visit 1b. All patients entering the Treatment Period, whether immediately upon study entry or following a period of time in the Observation Period, will initially be titrated to a dose that can be as high as 180 mg BID during the first 4 weeks of the Treatment Period (See [Table 3](#) for dosing schedule). Patients who continue in the Observation Period and maintain a Worst Itch NRS score of < 5 will be screen failed from the study at the end of the 12-week period. While patients remain in the Observation Period, they will not be considered as enrolled into the study, but as participating in an extended screening process until they are eligible for treatment.

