9.6.3 Observation Period (Extended Screening Weeks 1-12)

Only patients with Visit 1a Worst itch NRS score of less than 5 (<5) (Visit 1a for these patients is considered OV1) should enter the Observation Period, which includes subsequent study visits OV 2-4 at approximately one month intervals over the next 12 extended screening weeks (See [Table 7](#)). While patients remain in the Observation Period, they will not be considered enrolled into the study, but as participating in an extended screening process until they are eligible for enrollment. Patients evaluated at OV 2-4 and who record Worst itch NRS greater than or equal to 5 (≥ 5), and are otherwise eligible, can immediately begin Visit 1b and transition into the Treatment Period.

For these patients, the sum of time in the Observation Period and Treatment Period will not exceed 50 weeks. As a result, both the Observation Period and Treatment Period will differ in length for different patients. To ensure that the total number of study weeks does not exceed 50 weeks, that all patients complete proper titration of study drug up to the assessment of TV 2 during Treatment Week 3, and that the final Treatment Period visit is always TV14, see [Table 8](#) for visit details. As such, visits during this period are not equivalent to Treatment Weeks. During the Observation Period, patients are participating in Extended Screening Weeks.

9.6.3.1 *Observation Visit 2 at Extended Screening Week 4 and Observation Visit 3 at Extended Screening Week 8*

The following procedures are to take place at this visit:

- administer the Worst itch NRS
 - If the Worst Itch NRS is less than 5 (<5), perform the following Observation Visit procedures at any time during the visit
 - obtain vital signs
 - record AEs
 - record concomitant medications
 - If the Worst Itch NRS is greater than or equal to 5 (≥ 5), transition the patient to the Treatment Period and conduct Visit 1b procedures (described in [Section 9.6.4](#)) on the same day as this visit. See [Table 8](#) for a summary related to future Treatment Period Visits.

9.6.3.2 *Observation Visit 4 at Extended Screening Week 12*

The following procedures are to take place at this visit:

- administer the Worst itch NRS
 - If Worst Itch NRS is less than 5 (<5), perform the following Observation Visit procedures at any time during the visit
 - obtain vital signs
 - administer the following
 - Average itch intensity NRS
 - VRS
 - ItchyQoL
 - MOS Sleep-R
 - HADS
 - record AEs

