 - record concomitant medications
 - If the Worst Itch NRS is greater than or equal to 5 (≥ 5), transition the patient to the Treatment Period and conduct Visit 1b procedures (described in [Section 9.6.4](#)) on the same day as this visit. See [Table 8](#) for a summary related to future Treatment Period Visits.

Patients whose Worst Itch NRS is less than 5 (<5) at the OV4 should be screen failed from the study. No Washout/Safety follow-up visit is to take place.

9.6.3.3 *Transitioning from the Observation Period to the Treatment Period*

- For patients who have a Worst NRS score that is greater than or equal to 5 (≥ 5) at Observation Visit 2, 3, or 4, complete Visit 1b procedures (see [Section 9.6.4](#)).
- These patients will receive up to 46 weeks of study medication treatment.
- See [Table 8](#) for the Treatment Period Visits to be completed post Visit 1b, as well as the number of weeks of study drug to dispense at each Treatment Visit and when to schedule the End of Treatment Visit 14, TV14, to take place.
- See [Section 9.6.2](#) and the Schedule of Events ([Appendix 1](#)) for procedures to be performed at each applicable Treatment Visit.

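### The promised summary of Observation Period AEs cannot be built correctly on the dosed-only Safety Population that Version 1.0 prescribes for all safety analyses

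*Protocol*

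**What the plan says.** The Safety paragraph of the synopsis, in Version 1.0 and again in Version 2.0, makes two commitments. AE results are given as proportions: "The incidence of AEs will be summarized through the presentation of proportions by MedDRA body system classification and preferred term". Off-drug events before treatment get their own summary: "Summary statistics for AEs with onset during the Observation Period will be separately summarized". No denominator is named for that summary.

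Version 1.0 Section 19.9.1 supplies the only safety population: "The Safety Population will consist of all patients who have received a single dose of study medication". Its scope is stated without exception: "The Safety Population will be used in all safety analyses".

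The design splits patients at Visit 1a by Worst Itch NRS. In Version 2.0 (Section 9.2), "patients who have Worst Itch NRS that is ≥ 5 will enter the Treatment Period upon completion of Visit 1a"; the others go into an untreated Observation Period of up to 12 weeks. Section 9.6.3 says of them: "While patients remain in the Observation Period, they will not be considered enrolled into the study". Those still below the threshold at the last observation visit leave without a dose: "Patients whose Worst Itch NRS is less than 5 (<5) at the OV4 should be screen failed from the study". Version 1.0 has the same structure with a different cut-off (treatment if NRS is above 2, observation if 2 or less). In both versions AEs are recorded at OV2, OV3 and OV4 (Table 7 of Version 1.0; Section 9.6.3 of Version 2.0), and Version 1.0 Section 17.5 starts AE recording at consent.

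**The concern.** An AE with onset in the Observation Period can occur only in a patient who entered that period. The prescribed population is mismatched with that group in two ways.

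- It leaves out patients who were observed, had AEs recorded, and were then screen failed undosed.
- It includes patients who went straight to treatment at Visit 1a and had no Observation time.

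The protocol therefore fixes a rule that gives the wrong table for a summary it also promises. An SAP that obeys Section 19.9.1 reports a diluted proportion from an incomplete set of events. An SAP that uses a sensible denominator departs from the protocol.

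At stake is a secondary safety table covering up to 12 weeks off drug after TR03. Safety is the primary objective, and the synopsis says any safety inference will come from clinical review of such summaries. An understated off-drug proportion could mislead a reader who sets it beside the on-drug tables. AEs, including serious ones, in observed and never-dosed patients would have no place in a table restricted to the Safety Population.

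**Working it through.** The plan gives no figure to reproduce: there is no sample size calculation, expected rate or denominator for this summary.

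**Inputs**
- N = 60, the stated maximum (Section 6). I take all 60 as taking part.
- p = share entering Observation: not given, assumed. Section 9.2 expects about one-third of patients to come from TR03 placebo with high itch. If all of these (60/3 = 20) enter treatment directly, up to about 40 could enter Observation, so I take p up to 2/3.
- q = share of observed patients later dosed: not given, assumed.
- Observation-period AE incidence: assumed equal in observed patients who are and are not later dosed.

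**Formulas**
- Observed = 60p
- Observed and later dosed = 60pq
- Direct entrants = 60(1-p)
- Safety Population = 60(1-p) + 60pq
- Observed but omitted = 60p(1-q)
- Reported/true incidence = pq/(1-p+pq)

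**Results**

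| p | q | Observed | Observed and dosed | Direct entrants | Safety Population | Observed but omitted | Reported/true | Understatement |
|---|---|---|---|---|---|---|---|---|
| 0.2 | 0.5 | 12 | 6 | 48 | 54 | 6 | 6/54 = 0.11 | 89% |
| 1/3 | 0.5 | 20 | 10 | 40 | 50 | 10 | 10/50 = 0.20 | 80% |
| 0.5 | 0.5 | 30 | 15 | 30 | 45 | 15 | 15/45 = 0.33 | 67% |
| 2/3 | 0.5 | 40 | 20 | 20 | 40 | 20 | 20/40 = 0.50 | 50% |
| 2/3 | 1 | 40 | 40 | 20 | 60 | 0 | 40/60 = 0.67 | 33% |

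To illustrate the second row with an assumed true incidence of 30%: 6 of 20 observed patients have an AE. Three of those 6 are later dosed, so the table shows 3/50 = 6%.

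The two faults behave differently. Dilution occurs whenever there is any direct entrant (p below 1). Omission occurs whenever any observed patient is never dosed (q below 1). Under equal incidence omission loses events and patients together; if incidence differs between the two groups, it also biases the result, in a direction the documents do not allow us to predict.

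The range is not a bound. At p = 0.2 and q = 0.25 the ratio is 3/51 = 0.06.

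**Do direct entrants form the majority of the Safety Population?** Their share is (1-p)/(1-p+pq), which exceeds one half only if p < 1/(1+q). At p = 1/3, q = 0.5 it is 40/50 = 80%; at p = 2/3, q = 0.5 it is 20/40 = 50%; at p = 2/3, q = 0.75 it is 20/50 = 40%.

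**The case against.** The strongest reply is that the summary is described as separate, with no denominator stated, so it can be read as a specific provision that limits the general rule; choosing table denominators is normal SAP work. Version 1.0 Section 19.8.2 also shows that observation-only patients were not forgotten. This does not remove the conflict. The general rule is written for all safety analyses with no exception, and Section 19.8.2 covers discontinuation only. An SAP can fill a gap, but here it would have to override a stated rule.

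The second reply stands in part. The sentence fixing the population is from Version 1.0. The Version 2.0 text at hand stops at Section 10.2, and only its contents list shows that a Section 19.9.1 exists. The conflict is shown within Version 1.0; for Version 2.0 it is a point to check.

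Several stronger readings are tempting and are not supported.

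- A reader might infer that the denominator would consist mostly of patients never in Observation. That depends on p and q, which the documents do not give, and it fails in some plausible cases above.
- A reader might infer that the Observation Period holds the only off-drug AE data. It does not: the Washout visit records AEs, and Version 2.0 adds a telephone contact at 30 days for patients who stop drug prematurely.
- A reader might infer a bias in a planned comparison of on-drug and off-drug incidence. No such comparison is planned, and patients in Observation are selected for low itch, so they are an imperfect background group.

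The AEs themselves are still recorded; the problem lies in how they are tabulated.

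**Conclusion.** The point holds in limited form. Within Version 1.0, the dosed-only population applied to all safety analyses is incompatible with a correct summary of Observation-onset AEs. It omits observed patients who are never dosed and counts direct entrants who were never at risk in that period.

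The existence of the conflict follows from the text. Its size does not: the understatement of about 33-89% covers the five scenarios shown and rests on assumed p and q, equal incidence, and the Safety Population being used literally as the denominator.

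The primary endpoint, TEAEs in Treatment Weeks 5-50, is defined on treated patients and is not touched. This should be corrected before the tables are specified, but it does not threaten the main safety result.

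**What to change.** Define an Observation Period set: all consented patients who entered the Observation Period, whether or not they were later dosed. Use it as the denominator for AEs and SAEs with onset in that period, and add an exception for this summary to the Section 19.9.1 sentence. Check Version 2.0 Section 19.9.1 for the same sentence and amend it if present. Reporting patient-weeks of observation beside the proportions would help, because patients leave Observation at different visits, but it is optional.

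The cost is one population definition, one exception clause and one table denominator. No new data are needed, since AEs are already recorded at OV2 to OV4.

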2 LIST OF ABBREVIATIONS

Abbreviation	Definition
ACC	American College of Cardiology
AE	Adverse event
AHA	American Heart Association
ALT	Alanine aminotransferase
ANCOVA	Analysis of covariance
AST	Aspartate Aminotransferase
ATC	Anatomic and Therapeutic Class
BID	Twice daily
BMI	Body Mass Index
BP	Blood pressure
BPM	Beats per minute
BUN	Blood urea nitrogen
CFR	Code of Federal Regulations
CHF	Congestive Heart Failure
CNS	Central nervous system
CRF	Case report form
CRO	Clinical Research Organization
CTCAE	Common Terminology Criteria for Adverse Events
DSMB	Data Safety Monitoring Board
ECG	Electrocardiogram
eCRF	Electronic case report form
ER	Extended release
FDA	Food and Drug Administration
GCP	Good Clinical Practice
H&E	Hematoxylin and eosin
HADS	Hospital Anxiety and Depression Scale
HCG	Human chorionic gonadotropin
HCl	Hydrochloric acid
HD	Hemodialysis
H pylori	Helicobacter pylori
HR	Heart rate
ICF	Informed consent form
ICD-10	International Classification of Diseases, 10th revision

Abbreviation	Definition
ICH	International Conference on Harmonization
IFSI	International Forum for the Study of Itch
IRB	Institutional Review Board
IUD	Intra-uterine device
KOR	Kappa Opiate Receptor
LC-MS/MS	Liquid chromatography tandem mass spectrometry
MedDRA	Medical Dictionary for Regulatory Activities
MOR	Mu Opiate Receptor
MOS	Medical Outcomes Study
MITT	Modified Intent-To-Treat
NONMEM	Non-linear mixed effects modeling
NRS	Numerical Rating Scale
NYHA	New York Heart Association
OV	Observation Period Visit
OTC	Over-the-counter
PAS	Prurigo Activity Score
PBI-P	Patient Benefit Index, pruritus version
PD	Pharmacodynamic(s)
PK	Pharmacokinetic
PN	Prurigo Nodularis
PRO	Patient-Reported Outcome; In this study, PRO instruments administered at the site are as follows: NRS, VRS, ItchyQoL, PBI-P, MOS Sleep-R, HADS, SOWs
QoL	Quality of Life
RR	Respiratory rate
SAE	Serious adverse event
SD	Standard deviation
SOWS	Subjective Opiate Withdrawal Scale
TC	Telephone Call
TdP	Torsade de Pointes
TV	Treatment Period Visit
UP	Uremic Pruritus
VRS	Verbal Rating Scale
WHO	World Health Organization

3 INTRODUCTION

3.1 PRURIGO NODULARIS AND STUDY RATIONALE

3.1.1 General Information on Prurigo Nodularis

Prurigo Nodularis (PN) is an intensely pruritic dermatologic condition with the presence of papules as well as nodules with excoriations and ulcerations. The basis of PN is a pre-existing severe and chronic pruritus of various etiologies (see [Table 1](#)). The pruritus leads to scratching. However, the etiology or predisposing factors leading to the development of papules and nodules of PN are largely unknown (Eigelshoven et al 2009; Valdya and Schwartz 2008; Lee and Shumack 2005). Iking et al (2012) reports that in the past few years the hypothesis for the etiology of PN as being a reaction pattern due to a “vicious cycle of repeated itching and scratching” is gaining wider acceptance in the medical community.

With regard to the types of pre-existing chronic pruritus conditions that have been reported in PN patients, [Table 1](#) summarizes data reported by Iking et al (2012) in their study of PN patients (N=108). Pruritus secondary to multi-factorial etiologies (“Mixed Origin”) was the most common source attributed to the cause of the chronic pruritus. The majority of the “mixed origin” patients had a combination of dermatological and systemic diseases or a combination of several systemic disorders.

Iking et al (2012) did not attribute any cases of PN to an underlying diagnosis that was solely psychological in origin. In the subjects who were diagnosed with PN from mixed origin etiologies (summarized in [Table 1](#)), the authors attributed psychological factors related to chronic pruritus etiology to be present in 5.6% of the PN subjects categorized as having mixed (multi-factorial) origin pruritus. In a study focused on understanding psychosomatic/psychiatric dimensions related to chronic itch, Schneider et al (2006) reported on 44 PN patients. The authors stated that 34% of subjects had no accompanying psychiatric diagnosis and 46.8% were given a diagnosis of “psychological or behavioral factors associated with disorders classified elsewhere” (ICD-10 code F54) –indicating that psychological factors may play a role in the development and course of the condition. Payne et al (1985) reported psycho-social problems may have been relevant in about 33% of the studied 42 subjects that were adequately questioned.

Table 1: Etiology of Chronic Pruritus Reported in Prurigo Nodularis Patients (N=108)

Origin of Pruritus by Organ System	Number of Patients (%)	% Mixed with Organ Category Contribution to Chronic Pruritus	Most Common Disease
Mixed (pruritus of multi-factorial etiologies)	64 (59.3%)	Dermatological Disease (19.4%)	Atopic diathesis
		Systemic Diseases (70.9%)	Sorbitol Intolerance
			Lactose Intolerance
			Iron Deficiency
			H pylori Infection
			Diabetes Mellitus
			Renal Failure
			Neurological Disease (4.1%)
		Neuropathy	
		Psychological Factors (5.6%)	Psychological Factors (non-specific)
Origin of Pruritus by Organ System	Number of Patients (%)	Most Common Disease	
Dermatological	20 (18.5%)	Atopic diathesis/dermatitis	
Systemic	8 (7.4%)	Sorbitol Intolerance	
		Lactose Intolerance	
		Hepatitis C	
		H pylori infection	
		Iron Deficiency	
		Diabetes Mellitus	
Unknown	14 (13%)	-	
Neurological	2 (1.9%)	Brachio-radial Pruritus	
Psychological	0 (0%)	-	

Source: Iking et al (2012)

Iking et al (2012) reported that the median value of the NRS average intensity pruritus measured 8 on a rating scale with anchor points of zero (no pruritus)-10 (worst imaginable pruritus). Itch intensity scores ≥ 7 are considered severe in terms of itch intensity and itch intensity scores ≥ 3 are considered moderate in terms of itch intensity (Stander et al 2013). Accioly-Filho et al (2000) reports that once the cycle of pruritus-excoriation-pruritus begins, it is difficult to stop as PN is very resistant to therapeutic intervention strategies. Papoiu et al (2013) report a central nervous system relationship to the itch-scratch cycle. The authors showed that there is a complex interaction of sensory, motor and emotional

components based on their investigation of using real-time flare brain MRI imaging and psychophysical ratings of itch relief or pleurability of scratching conducted in healthy volunteer experimental subjects.

Eigelshoven et al (2009) reports that patients present with excruciating pruritus that is usually anatomically symmetrical and mainly involves the extensor aspects of the extremities, the shoulders, chest and sacral regions with the appearance of typical lesions. Payne et al (1985) reported in a study of 46 subjects that the patients came from all social classes and racial groups, almost equally divided by gender and with a mean age of 39.5 years at the time of PN onset. Iking et al (2012) reported in their study that the patients were distributed in age between 11.9 years - 95.6 years with a median age of 61.9 years and there were more females than males affected by the disease.

Weigelt et al (2010) summarized the characteristic histological findings in PN that include the presence of thick compact orthohyperkeratosis; folliculosebaceous units in nonvolar skin in conjunction with a thick and compact cornified layer; irregular epidermal hyperplasia or pseudoepitheliomatous hyperplasia; focal parakeratosis; hypergranulosis; fibrosis of the papillary dermis with vertically arranged collagen fibers; increased number of fibroblasts and capillaries; a superficial, perivascular and/or interstitial inflammatory infiltrate of lymphocytes, macrophages and, to a lesser extent, eosinophils and neutrophils.

In terms of treatment options for PN, there have been a variety of medical interventions discussed. Hogan et al (2012) recently reviewed the therapies discussed in the literature that included topical, systemic and intra-lesion steroids administration; antihistamines; anxiolytics; opiate receptor antagonists; thalidomide; gabapentin; capsaicin cream; topical anesthetics; occlusive therapies; ultraviolet light; and reports that they had “mild to moderate success at best”. The authors also comment on the potential imbalance in the mu-kappa opiate receptor system and mention the possibility of studying the kappa agonist nalfurafine (see [section 3.1.3.1](#), where nalfurafine was used as a positive control in Sponsor’s preclinical substance P mouse model of itch investigation). Spring et al (2014) reported on the use of methotrexate and the need for chemotherapeutic related regular medical monitoring. Liu et al (2013) and Kanavy (et al 2012) both reported on lenalidomide is case reports, but the drug led to side effect of a reversible myopathy in one of the subjects. Accioly-Filho (2000) reported the condition is “notoriously resistant to therapy”. Iking et al (2012) and Valdyia and Schwartz (2008) reported a significant impact on the patient’s quality of life (2008). Spring et al (2014) report PN to be debilitating condition and a therapeutic challenge where conventional treatments with steroids, standard anti-pruritic agents, phototherapy and immune-suppressors often fail.

